### **2.2.3. Nonclinical Safety**

PF-07081532 has been evaluated in a comprehensive nonclinical safety package that includes toxicity studies up to 6 months (in rats) and 9 months (in monkeys), as well as reproductive and developmental toxicology studies in rats and rabbits. Based on the nonclinical studies conducted, the target organs and systems identified with PF-07081532 administration include the heart, stomach and liver.

In the 6-month pivotal study with 1-month recovery phase in rats, oral gavage administration of PF-07081532 for 6 months did not result in any mortality or adverse effects in any of the study parameters or endpoints evaluated resulting in the high dose being the NOAEL. The exposure at this dose provided exposure margins of 40 $\times$  and 29 $\times$  ( $C_{max}$  and AUC24, respectively) over the highest clinical dose planned (260 mg QD).

In the 9-month pivotal study in cynomolgus monkeys, PF-07081532 was administered by oral gavage with doses titrating up. There were no adverse findings in the endpoints evaluated in this study. The primary effects were consistent with the expected pharmacology of the test article which included decreased body weight associated with decreased food consumption, and secondary changes in clinical chemistry and hematology parameters. At the NOAEL dose, the exposure margins were 5.2× and 4.6× ( $C_{max}$  and  $AUC_{24}$ , respectively) over the highest clinical dose (260 mg QD) planned.

The NOAELs in the 6-month rat or 9-month monkey pivotal toxicity studies were 100 mg/kg/day in both species, with associated unbound  $C_{max}$  of 768 ng/mL and unbound  $AUC_{24}$  of 8270 ng•h/mL in rats and unbound  $C_{max}$  of 98.5 ng/mL and unbound  $AUC_{24}$  of 1300 ng•h/mL in monkeys.

PF-07081532 was not genotoxic in either in vitro or in vivo assays. In addition, PF-07081532 was negative in the 3T3 Neutral Red uptake Phototoxicity Test, indicating that PF-07081532 is not phototoxic.

Refer to the IB for more details on the nonclinical safety of PF-07081532.

#### **2.2.4. Clinical Overview**

As of issuance of this protocol, 2 Phase 1 studies evaluating PF-07081532 (C3991001 and C3991002) have been completed. In total, 88 participants have been randomized, including 22 healthy adult participants, 51 adult participants with T2DM, and 15 adult participants with obesity. A total of 74 unique participants have been exposed to at least 1 dose of PF-07081532. The safety profile of PF-07081532 was assessed in these 2 completed clinical studies and, to date, administration of PF-07081532 at single doses up to 200 mg and multiple doses up to 180 mg QD has been considered safe, with the majority of the TEAEs being mild in intensity.

One Phase 1 study, C3991003, recently concluded. This inpatient study enrolled participants with T2DM inadequately controlled on metformin, and participants with obesity, to receive PF-07081532 or placebo QD for 42 days. The starting dose for the first cohort of this study was 20 mg QD of PF-07081532, with subsequent dose levels determined based on emerging data; the maximum dose administered was 80 mg QD. While final clinical data from this study are not yet available, as of issuance of this protocol, there have been no deaths, SAEs or AEs of severe intensity reported.

Refer to the IB for more details on the clinical safety of PF-07081532.

##### **2.2.4.1. Clinical Pharmacokinetics**

The clinical PK of PF-07081532 in adult participants have been evaluated to date in 2 completed studies (C3991001 and C3991002). The results of these completed studies are summarized in the PF-07081532 IB.

In Study C3991001 following administration of single oral doses of PF-07081532 under fasted conditions to healthy participants, PF-07081532 was absorbed relatively rapidly with a

median  $T_{max}$  of 1.00 to 4.02 hours (individual  $T_{max}$  values ranged between 0.5 and 6 hours). Based on the individual plasma concentration-time profiles, the absorption phase exhibited multiple peaks, especially at the higher dose levels. Mean  $t_{1/2}$  ranged from 18.03 to 20.90 hours across all doses. Plasma  $C_{max}$  increased less than proportionally across the entire investigated dose range (from 10 mg to 200 mg), while plasma  $AUC_{inf}$  increased less than proportionally from 10 mg to 30 mg and approximately proportionally from 30 mg to 200 mg. Inter-participant variability for PF-07081532 exposure was low to moderate and ranged from 9% to 36% CV for  $C_{max}$  and 15% to 44% CV for  $AUC_{inf}$  across all doses. Overall, the results indicate that PF-07081532 may be administered without regard to food.

In Study C3991002 following administration of PF-07081532,  $C_{max}$  was observed at 1 to 2 hours on Day 1, and 2 to 8 hours following the last dose on Day 28 or 42. Across all dose groups, the mean  $t_{1/2}$  ranged from 20.70 to 26.50 hours. PF-07081532 exposure generally increased in an approximately dose-proportional manner across the dose range studied, and accumulation of less than 2.1-fold was observed. Urinary recovery of unchanged PF-07081532 was low, with less than 0.2% of the dose recovered in the 24-hour dosing interval following last dose administration. Interparticipant variability for PF-07081532 exposure ranged from 17% to 51% CV for  $C_{max}$  and 15% to 62% CV for  $AUC_{tau}$  across all doses. No substantial differences in PF-07081532 exposure ( $C_{max}$  and  $AUC_{tau}$ ) were observed between participants with T2DM and obesity either after single dose (Day 1, 10 mg) or multiple dose (Day 28, 120 mg and Day 42, 180 mg) administration.

In Study C3991003 following single-dose (Day 1) and multiple-dose (Day 42) administration of PF-07081532, peak plasma PF-07081532 concentrations ( $C_{max}$ ) were observed at 1 to 2 hours and 2 to 5 hours, respectively. Terminal  $t_{1/2}$  averaged 24.37 to 26.04 hours following multiple-dose administration (Day 42). PF-07081532 exposure ( $C_{max}$  and  $AUC_{tau}$ ) increased in an approximately dose-proportional manner across the dose range studied. Accumulation with QD dosing was less than 2-fold. No substantial differences were observed in the achieved exposures (both  $C_{max}$  and  $AUC_{tau}$ ) between participants with T2DM and obesity either after single-dose (Day 1, 20 mg) or multiple-dose (Day 42, 60 mg) administration.

Refer to the IB for more details on the clinical PK of PF-07081532.

### **2.3. Benefit/Risk Assessment**

PF-07081532 is not expected to provide any clinical benefit to healthy participants. This study is designed primarily to generate safety, tolerability, and pharmacokinetic data for further clinical development.

More detailed information about the known and expected benefits and risks and reasonably expected AEs of PF-07081532 may be found in the IB, which is the SRSD for this study. The SRSD for the site sourced itraconazole and cyclosporine capsule products are the corresponding USPIs.

### 2.3.1. Risk Assessment

Potential Risk of Clinical Significance	Summary of Data/Rationale for Risk	Mitigation Strategy
Study Intervention: PF-07081532		
Thyroid C-cell tumors	
The potential risks are based on product labeling for injectable GLP-1R agonists (ie, liraglutide, dulaglutide, semaglutide, and exenatide) due to dose-dependent and treatment duration-dependent thyroid C-cell tumors in nonclinical studies in rats and mice at clinically relevant exposures.
 
Of note, similar tumors were not seen in rodent studies with PF-07081532, likely as PF-07081532 does not stimulate rodent GLP-1 receptors.
	
Potential participants with a personal or family history of medullary thyroid carcinoma or Multiple Endocrine Neoplasia syndrome type 2 are excluded from the clinical development program.
 
Thyroid function tests are included in the clinical trial protocols to monitor participants' thyroid function.

Pancreatitis	
The potential risks are based on product labeling for injectable GLP-1R agonists (ie, liraglutide, exenatide, semaglutide and dulaglutide).
 
One SAE of obstructive pancreatitis has been observed in the PF-07081532 clinical trial program, which was considered to be treatment-related by the investigator, but unrelated by the sponsor.
	
Per exclusion criteria, potential participants with acute pancreatitis or a history of chronic pancreatitis are not eligible for study entry.
 
Serum amylase and lipase are monitored during clinical studies.

Hypoglycemia	
Clinical trials with injectable GLP-1R agonists have not demonstrated an increased risk for hypoglycemia. But when administered in combination with anti-diabetic agents that are known to have an increased risk of hypoglycemia (such as insulin or sulfonylureas), an increased risk for hypoglycemia was observed.
 
Participants with obesity who do not have co-existing T2DM would not be taking anti-diabetic agents and therefore would not be expected to have an increased risk for hypoglycemia.
 
A low overall frequency of generally mild hypoglycemia has been reported in the PF-07081532 clinical development program to date.
	
Anti-diabetic medications are prohibited in this study, and blood glucose is monitored as a part of the lab assessments during the study.
 
Participants are informed about the signs and symptoms of hypoglycemia and are monitored for these symptoms during the study.

Potential Risk of Clinical Significance	Summary of Data/Rationale for Risk	Mitigation Strategy
Impairment in renal function	
Potential risks are based on product labeling for injectable GLP-1R agonists, and predominantly occur in patients with significant nausea, vomiting, and dehydration.
 
In the clinical trial program only one mild adverse event (Preferred Term Blood creatinine increased) has been observed.
	
Per exclusion criteria, potential participants with significant renal impairment are not eligible for study entry.
 
Renal function is monitored by lab assessments of serum urea, creatinine and eGFR.
 
Hydration will be encouraged, and reduced fluid intake and evidence of dehydration, if detected, will be treated by close clinical follow-up.

Gastrointestinal adverse reactions	
The potential risks are based on product labeling for injectable GLP-1R agonists (ie, liraglutide, exenatide, semaglutide and dulaglutide).
 
Gastrointestinal AEs, the majority of which were mild in severity, have been observed in the clinical program with PF-07081532. In nonclinical studies with PF-07081532, gastrointestinal adverse effects were observed in rats and monkeys.
	
Participants are monitored during the clinical studies to prevent potential sequelae of any severe gastrointestinal reactions, eg, dehydration.
 
Hydration will be encouraged and concomitant medication for nausea is permitted in the study.

Diabetic retinopathy complications	
The potential risk is based on the product labeling for the injectable GLP-1R agonist semaglutide and dulaglutide in patients with T2DM.
 
There are no nonclinical or clinical data involving PF-07081532 to suggest an increased risk of diabetic retinopathy complications.
	
Potential participants with diabetes mellitus are excluded from this clinical study.

Suicidal ideation and behavior	
The potential risk is based on the product labeling for the injectable GLP-1R agonists liraglutide and semaglutide for obesity based on long-term studies.
 
Suicidal ideation has not been observed in the PF-07081532 clinical studies to date.
	
Suicidal ideation and behavior, along with symptoms of depression, will be monitored at specified intervals during the study using the C-SSRS and PHQ-9 questionnaires, with referral to a MHP for further evaluation if needed.

Changes in heart rate	
Potential risk is based on the product labeling for the injectable GLP-1R agonists, liraglutide and semaglutide, for T2DM and obesity.
 
Modest increases in HR have been noted in the early clinical studies with PF-07081532, with most values remaining within the normal range.
	
HR is monitored during the clinical study.

Potential Risk of Clinical Significance	Summary of Data/Rationale for Risk	Mitigation Strategy
Declines in body weight	Decreased appetite and body weight loss have been reported for marketed GLP-1R agonists and declines in body weight have been noted at higher doses of PF-07081532.	Weight is collected at multiple timepoints and will be monitored throughout the trial.
Acute gallbladder disease	Potential risk is based on the product labeling for the injectable GLP-1R agonists, semaglutide and liraglutide, for T2DM and obesity.  Acute gallbladder disease has not been observed in the PF-07081532 clinical trial program to date.	Participants with symptomatic gallbladder disease are excluded from this clinical study.  Participants are monitored for AEs and laboratory tests that may suggest development of acute gallbladder disease.
Study Intervention: Itraconazole		
Rare cases of serious hepatotoxicity, including liver failure and death. There have been reports of congestive heart failure. In post-marketing experience, heart failure was more frequently reported in patients receiving a total daily dose of 400 mg although there were also cases reported among those receiving lower total daily doses. Transient or permanent hearing loss has been reported in patients receiving treatment with itraconazole.	Risk based on product labeling.	Multiple oral doses of 200 mg QD for 9 days are administered in this study and pose minimal risk. Participants will be monitored in an inpatient clinical research unit.
Study Intervention: Cyclosporine		
Systemic hypertension, hepatotoxicity and nephrotoxicity; the risk increases with increasing dose and duration of cyclosporine therapy. Renal dysfunction, including structural kidney damage, is a potential consequence of cyclosporine, and therefore, renal function must be monitored during therapy.	Risk based on product labeling.	A single oral dose of 600 mg is administered in the study and poses minimal risk. Participants will be monitored in an inpatient clinical research unit.  Hydration will be encouraged and concomitant medication for nausea is permitted in the study.

Potential Risk of Clinical Significance	Summary of Data/Rationale for Risk	Mitigation Strategy
Other		
Risk of COVID-19 exposure during study	Study participants could be infected with the SARS-CoV-2 virus during study participation. This could lead to increased health risk for this participant and others in the study.	Participants undergo COVID-19 specific assessments at admission to study site and when symptoms arise.

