**Table 1. Study Schedule of Assessment**

Visit Identifier' Abbreviations used in this table may be found in Annex 9 .	Screen	Period 1		Period 2	Period 3	F/U (Phone Call)	ET	Notes
Study Day		-1	to 5	6 to 10	11 to 20	28 to 54		
Days Relative to Day 1	D-28 to D-2	D-1	D1 to D5	D1 to D5	D1 to D10	28-35 Days		1. All screening should be done 28 days before the first dose. 2. Day relative to start of study intervention (Day 1). 3. In this study, follow-up is to be conducted via phone contact 28 to 35 days after administration of the final dose of study intervention (Period 3 Day 9, Study Day 19).
Safety laboratory (hematology, chemistry, and UA)	X	X		X (D5 chemistry only)	X		X	
 
See Table 5 for a complete list of clinical lab tests.
 
Period 3 collection prior to discharge on Day 10.
 

Calcitonin, amylase, lipase, HbA1C, TSH, C-Peptide	X							
 
An overnight fast is required prior to calcitonin sample collection.
 

Demography	X							
 
Including height and weight.
 

Serum and urine pregnancy test (WOCBP only)	X	X			X (D10)		X	
 
Pregnancy tests will also be done whenever 1 menstrual cycle is missed during the active treatment period (or when potential pregnancy is otherwise suspected) and at the end of the study prior to discharge on Period 3 Day 10.
 

Contraception check	X	X				X	X	
FSH	X							
 
For any female who has been amenorrheic for at least 12 consecutive months.
 

Urine drug testing	X	X						
 
Participants may undergo random urine drug testing at the discretion of the investigator.
 

Single 12-Lead ECG	X		X	X	X		X	
 
Pre-dose Day 1 in each period, and prior to discharge on Period 3 Day 10.
 

Blood pressure, pulse rate, and body temperature	X		X	X	X		X	
 
Pre-dose Day 1 in each period, and prior to discharge on Period 3 Day 10.
 
Body temperature will be taken at Screening only.
 

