**Table 5. Protocol-Required Safety Laboratory Assessments**

Hematology	Chemistry	Urinalysis	Other
Hemoglobin Hematocrit RBC count Platelet count WBC count Total neutrophils (Abs) Eosinophils (Abs) Monocytes (Abs) Basophils (Abs) Lymphocytes (Abs)	Urea and creatinine Cystatin C and eGFR Glucose (fasting) Calcium Sodium Potassium Chloride Total CO 2 (bicarbonate) AST, ALT TBili Alkaline phosphatase Uric acid Albumin Total protein	Local dipstick: pH Glucose (qual) Protein (qual) Blood (qual) Ketones Nitrites Leukocyte esterase  Laboratory: Microscopy and culture a	
 
• Urine drug screeningb
 
• Pregnancy test (β-hCG)c
 
• COVID-19 testing
 
 
At Screening:
 
 
• FSHd
 
• HIV, HbsAg, HCVAb, HbcAb, HCV RNAe
 
• HbA1C
 
• TSH
 
• Calcitonin
 
• C-peptide
 
• Amylase and lipase
 

	
Required:                      For suspected DILI:                      AST/ALT                      TBili, direct and indirect bili                      Total bile acids, GGT                      Total protein, albumin                      CK                      PT, INR                      Acetaminophen/paracetamol                      or                      protein adduct levels                      Hepatitis serology (even if screening negative)
		

- Only if UTI is suspected and urine dipstick is positive for nitrites or leukocyte esterase or both.
- The minimum requirement for drug screening includes cocaine, THC, opiates/opioids, benzodiazepines, and amphetamines (others are site and study specific).
- Serum or urine β-hCG for female participants of childbearing potential.
- For confirmation of postmenopausal status only.
- The test will be performed if HCV is positive.

The investigator must review the laboratory report, document this review, and record any clinically relevant changes occurring during the study in the AE section of the CRF.

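### Amylase and lipase monitoring is listed as a pancreatitis safeguard, but both are scheduled at Screening only: add them to post-dose chemistry already drawn

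*Protocol*

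**What the plan says.** Protocol Section 2.3.1 gives two mitigations for pancreatitis. One is exclusion by history. The other reads "Serum amylase and lipase are monitored during clinical studies". The same row reports one SAE of obstructive pancreatitis in the programme, which the investigator considered related to treatment and the sponsor did not.

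In Table 1, the row "Calcitonin, amylase, lipase, HbA1C, TSH, C-Peptide" has a single mark, in the Screening column. In Table 5, "Amylase and lipase" appears in the Other column under the Screening sub-heading, and the Chemistry column omits both. The only stated use of the results is in Section 5.2, criterion 23, which excludes participants with either enzyme above ULN at Screening.

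The row beginning "Safety laboratory (hematology, chemistry, and UA" is marked at Screening, Day -1, Period 2, Period 3 and early termination (ET). The Period 2 entry is "X (D5 chemistry only" and the note for Period 3 is "Period 3 collection prior to discharge on Day 10". Section 8.3.4 also permits unscheduled laboratory tests for a perceived safety issue, without naming these enzymes. The SAP adds no amylase or lipase assessment.

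**The concern.** A test done once before dosing, to decide eligibility, is not monitoring. Someone reading the benefit/risk table, such as an ethics committee member or an investigator, would take it that enzyme results will be available while participants are on drug. None is scheduled. Section 2.3.3 rests its benefit/risk conclusion on the risk-minimising measures, so a listed measure that the trial does not carry out weakens that statement.

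The trial also gives PF-07081532 with two inhibitors that may raise its exposure, which is why Section 4.3 chose a conservative 40 mg dose. The participants are not expected to gain clinical benefit. What is at stake is the accuracy of a stated safeguard and a small amount of safety information. No estimate or confidence interval is involved.

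**Working it through.** The plan gives no figure to reproduce. The check sets the text against the schedule and then counts.

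**1. Scheduled enzyme values now**
- Table 1: one time point, at Screening, before any dose.
- PF-07081532 doses: Period 1 Day 1 (Study Day 1), Period 2 Day 1 (Study Day 6) and Period 3 Day 4 (Study Day 14).
- Scheduled amylase or lipase values after any of these: 0.

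**2. How other rows of Section 2.3.1 compare**
- Glucose and renal function are also described as monitored. Both are in the Table 5 chemistry panel, which is drawn after dosing at Period 2 Day 5 and Period 3 Day 10. For these, text and schedule agree.
- The thyroid row says "Thyroid function tests are included in the clinical trial protocols to monitor" thyroid function. TSH is on the same Screening-only line of Table 1, so that row has the same mismatch.

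**3. Existing draws that could carry the two analytes**
- Period 2 Day 5 is Study Day 10. Time since that period's dose: (5 - 1) × 24 = 96 h.
- Period 3 Day 10 is Study Day 20. Time since that period's dose: (10 - 4) × 24 = 144 h.
- From the Period 2 draw to the third PF-07081532 dose: 14 - 10 = 4 days.
- Period 1 has no post-dose chemistry draw, so the first on-treatment value would follow two doses.

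**4. Results gained**
- Per completer: 2 draws × 2 analytes = 4.
- For 12 completers: 12 × 4 = 48.
- For about 16 enrolled, if all complete: 16 × 4 = 64, with ET draws for anyone who leaves early.

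**5. Incidental elevations**

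The documents give no rate. If 1% to 5% of results were above ULN by chance (an assumption), 64 results would give 64 × 0.01 = 0.64 to 64 × 0.05 = 3.2.

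**6. Comparator**

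Table 1 says "All screening should be done 28 days before the first dose", with a window of Day -28 to Day -2. Section 8.1 lets the interval run longer without rescreening if pre-dose laboratory results meet eligibility. The Screening value may therefore be several weeks old when it is compared with a post-dose value.

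**The case against.** The strongest reply is that the sentence describes the programme. It refers to clinical studies in the plural and without an article, and the thyroid row above it speaks of the development programme. Rows that make a promise for this trial mostly say so, for example those on hypoglycaemia, heart rate and body weight. Conduct is also not in doubt: the schedule governs timing, and Table 1, Table 5 and criterion 23 agree, so no site would be misled.

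Much of this stands, and it is why the severity is low. It does not remove the mismatch. The gastrointestinal row also uses the plural for monitoring that applies here, and the sentence sits in this protocol's own mitigation column. If it does describe the programme, this trial departs from the practice it cites without saying so.

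A second reply is that the risk is already handled, and this is largely right. Participants with a pancreatitis history or raised enzymes are excluded, they are confined to Study Day 20, adverse events are elicited for at least 28 days after the last dose, and unscheduled tests are allowed. Earlier single doses up to 200 mg were considered safe. A reader might infer that pancreatitis risk is left unmitigated or that the trial is unsafe. The documents do not support that.

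A third reply is that new tests have consequences. Under Section 10.3.1, an abnormal result that needs further diagnostic testing must be recorded as an AE, so incidental elevations could enter the TEAE summaries. A Day -1 test would be worse: Table 1 repeats the eligibility check that day, and no rule covers a raised enzyme value then. Both points are accepted, and Day -1 is left out of the fix.

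**Conclusion.** The point holds at low severity. Section 2.3.1 names enzyme monitoring as a safeguard, and the schedule contains 0 post-dose values across three doses. Using chemistry already drawn would raise this to 2 post-dose time points, or 4 results per completer, plus ET where it applies.

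The gain is modest. At about 96 h and 144 h the draws can show a rise that persists but not one near peak exposure. There is no value specific to Period 1, and only the Period 2 result precedes another PF-07081532 dose. That result could inform the third dose if it is reported within the 4 days, which is an assumption about laboratory turnaround. Section 7.1 has no enzyme-based stopping rule, so any action would come under its general provision for safety concerns.

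Two further inferences are not supported. The matching thyroid mismatch does not call for on-study thyroid tests: Section 2.3.1 describes that risk as dependent on dose and treatment duration, and this trial gives three single doses. Nothing here touches the primary PK analysis or the sample size.

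**What to change.** Add amylase and lipase to the safety chemistry at Period 2 Day 5, Period 3 Day 10 and ET, and amend Table 1 and Table 5 to match. Keep the Screening value as both eligibility test and comparator, and add no Day -1 test. Clinically significant abnormal values follow the repeat-test rule already in Section 8.3.4, so no new threshold is needed.

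Two small edits make the comparator usable. Section 9.3.2 treats Screening laboratory data used for eligibility as source data that need not be reported, so the amendment should ask for these two values to be captured. SAP Section 3.5.2 takes baseline from Period 1 Day 1, so it should name Screening as the baseline for these two tests.

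Cost: two analytes on draws already planned, with no new visit or venepuncture. Planned blood volume is about 200 mL against a cap of 550 mL in 56 days. A few incidental elevations may need repeating and could be recorded as AEs. The change needs a protocol amendment and, under Section 10.1.1, IRB/EC approval before it is implemented.

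If the sponsor intends Screening-only testing, the amylase/lipase and thyroid sentences in Section 2.3.1 should state that these tests are done at Screening for eligibility and that later tests are unscheduled. That costs a wording edit and adds no safety information.
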